8.2.3.6 Overall Survival (OS)

OS is defined as the time from date of enrollment to death due to any cause. For patients last known to be alive, OS will be censored at date of completion/discontinuation.

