7.2.3. Duration of the study

According to MFDS re-examination regulation, the re-examination report based on collected data of 6 years must be submitted to MFDS within 3 months after the end of specified re-examination period (from the product approval date to 6 years afterwards).

The data collection period of this study is until the required subject number (100 patients) is collected. The observation period for each subject is from initiating administration of first dose of BESPONSA® to the end of the observation period of the study, which must include at least 28 calendar days following the last administration of a BESPONSA®. In case of patient that Hematopoietic Stem Cell Transplant (HSCT) after administrated BESPONSA®, follow-up until 180 days after transplantation. All the data collected during the observation period should be recorded in the case report form (CRF). In case of an adverse event/safety event recognized after the observation period ends, it should be recorded in the CRF as specified in Section 7.

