9.2. Reporting period

For each patient, the safety event reporting period begins at the time of the patient's first dose of BESPONSA®, or the time of the patient's data privacy statement if s/he is already exposed to BESPONSA®, and lasts through the end of the observation period of the study, which must include at least 28 calendar days following the last administration of a drug under study; a report must be submitted to Pfizer Safety (or its designated representative) for any of the types of safety events listed in the table above occurring during this period. If a patient was administered a drug under study on the last day of the observation period, then the reporting period should be extended for 28 calendar days following the end of observation.

Most often, the date of data privacy statement is the same as the date of enrollment. In some situations, there may be a lag between the dates of data privacy statement and enrollment. In these instances, if a patient provides data privacy statement but is never enrolled in the study (e.g., patient changes his/her mind about participation), the reporting period ends on the date of the decision to not enroll the patient.

If the investigator becomes aware of a SAE occurring at any time after completion of the study and s/he considers the SAE to be related to BESPONSA®, the SAE also must be reported to Pfizer Safety.

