5.1 SAFETY ANALYSIS SET

The safety analysis set includes patients who have been administered BESONSA® at least once and evaluated with safety-related endpoints at least once.

Patients meeting any of the following criteria will be excluded in the safety analysis set.

1. Patients who received BESONSA® prior to site initiating contract date
2. Patients who didn't receive BESONSA®
3. Safety follow-up failure: Patients without documented evidence for whom adverse event status was evaluated(Patients with "Whether AE status was evaluated" checked as No in the eCRF OR no answer is provided to question "Whether a patient has AE" in the eCRF)
4. Patients who violated inclusion/exclusion criteria
5. Patients who violated usage
6. Patients who have enrolled twice or more (i.e. if a patient has been assigned to two or more subject ID or CRFs, only one record clarified by site will be used for analysis and the others will be excluded)

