8.2.3.5 Progression-free survival (PFS)

PFS is defined as time from date of enrollment to earliest date of the following events:

PFIZER CONFIDENTIAL

CT24-WI-GL03-RF02 3.0 *Non-Interventional Statistical Analysis Plan for Primary Data Collection Study*
Page 14 of 17

- Death
- Refractory disease
- Progressive disease
- Relapsed disease

Subjects without a PFS event at time of analysis will be censored at the last valid disease assessment. In addition, subjects with documentation of an event after an unacceptably long interval (>28 weeks if there was post-baseline disease assessment, or >12 weeks if there was no post-baseline assessment) since the previous disease assessment will be censored at the time of the previous assessment (date of enrollment if no post-baseline assessment). Post-study treatment follow-up disease assessments will be included.

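### PFS and OS start at an undefined enrollment date although patients may enter after their first dose, so time zero is not the same event for every patient and some PFS times can be zero or negative

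*SAP*

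**What the plan says.** The survival endpoints appear in the part of SAP 8.2.3 written for a manuscript. For PFS: "PFS is defined as time from date of enrollment to earliest date of the following events"; the listed events are death and refractory, progressive or relapsed disease. For OS: "OS is defined as the time from date of enrollment to death due to any cause". Neither clause says what the enrollment date is. The PFS censoring rule falls back on the same date when there is no post-baseline assessment.

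Other sections bear on who enters and when:

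- Protocol 7.2.3 uses a different origin: "The observation period for each subject is from initiating administration of first dose of BESPONSA".
- Protocol 9.2 starts safety reporting at first dose, or at the privacy statement "if s/he is already exposed to BESPONSA". It adds that "there may be a lag between the dates of data privacy statement and enrollment".
- SAP 5.1 limits late entry in one way only, by excluding "Patients who received BESONSA® prior to site initiating contract date".
- Protocol 7.2 leaves entry to the physician's discretion. The eligibility criteria (Protocol 7.2.1 and 7.2.2) contain no rule that enrollment must come at or before the first dose.
- SAP 8.2.3 places effectiveness analyses in the effectiveness set, and SAP 5.2 removes from that set anyone with no response evaluation.

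**The concern.** A survival curve needs one time zero. Here a patient who enrolls on the day of first dose is followed from the start of treatment. A patient who enrolls several weeks later is followed from some point during or after treatment. Both contribute to the same curve, and the SAP has neither a delayed-entry adjustment nor a sensitivity analysis from first dose.

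Two consequences follow for patients who enter late.

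1. A patient who would have enrolled late but dies first cannot be in the data. The documents give no means of counting such patients.
2. A patient who is found refractory or progressive before enrolling can still enroll, because no criterion prevents it and the CRF records the response after every cycle (Protocol 7.3.6). The earliest PFS event then falls on or before time zero, and the SAP does not say what to do.

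The published PFS and OS curves would be read as survival from the start of BESPONSA, which they would not strictly estimate.

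**Working it through.** The plan gives no survival estimate, event target or power for these endpoints, so there is no figure to reproduce. The check has one logical step and three numerical ones.

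**Inputs from the documents.** Median survival of 3-6 months (Protocol 5, SAP 2). This is general background for adults with relapsed or refractory disease, not a figure for patients on BESPONSA, and it is used only for scale.

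**Assumptions not in the documents.** Lag L from first dose to enrollment of 2-12 weeks. Share q of would-be participants who enroll late of 25-100%. Weibull survival S(t) = exp(-ln2 × (t/m)^k) with median m and k = 0.7 (hazard highest early), 1.0 (constant) or 1.3 (rising). One month = 4.348 weeks, so m = 13.04 or 26.09 weeks.

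**Step 1. Can a PFS time be negative?** Yes. Suppose first dose is at week 0, a refractory evaluation at week 3 and enrollment at week 4. PFS = 3 - 4 = -1 week.

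**Step 2. Deaths before entry.** Under a constant hazard, the share of would-be late enrollers who die before they can enroll is 1 - 0.5^(L/m). For L = 4 weeks and m = 3 months: 1 - 0.5^(4/13.04) = 0.191.

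| Lag | m = 3 months | m = 6 months |
|---|---|---|
| 2 weeks | 10.1% | 5.2% |
| 4 weeks | 19.1% | 10.1% |
| 8 weeks | 34.6% | 19.1% |
| 12 weeks | 47.1% | 27.3% |

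These are shares of late enrollers only. If half would enroll 4 weeks late, the loss from the whole group is 0.5 × 19.1% = 9.6% or 0.5 × 10.1% = 5.0%.

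**Step 3. Effect on the median by the enrollment clock.** The median t solves

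[(1-q)S(t) + q·S(L+t)] / [(1-q) + q·S(L)] = 0.5.

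Under a constant hazard S(L+t) = S(L)·S(t). The bracket in the denominator cancels and the left side is S(t), so the median does not change whatever q and L are.

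Example with k = 0.7, m = 3 months, L = 8 weeks, q = 1: (8/13.04)^0.7 = 0.710. The median solves ((t+8)/13.04)^0.7 = 1.710, so t + 8 = 13.04 × 1.710^(1/0.7) = 28.1 weeks. Then t = 20.1 weeks = 4.6 months.

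Over q = 25-100% and L = 4-8 weeks:

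| Hazard | True median 3.0 months becomes | True median 6.0 months becomes |
|---|---|---|
| Constant (k = 1.0) | 3.0 | 6.0 |
| Early-peaking (k = 0.7) | 3.2-4.6 | 6.3-8.2 |
| Rising (k = 1.3) | 2.3-2.9 | 5.1-5.9 |

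**Step 4. Which correction works?** Case: half enroll 8 weeks late, medians in months. The first two result columns are calculated; the last is one simulation of 6,000 would-be participants per row, before deaths prior to entry are removed.

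| True median | k | Enrollment clock | First dose, no delayed entry | First dose with delayed entry |
|---|---|---|---|---|
| 3.0 | 1.0 | 3.00 | 3.82 | 3.03 |
| 3.0 | 0.7 | 3.59 | 4.42 | 2.84 |
| 6.0 | 1.0 | 6.00 | 6.87 | 6.12 |
| 6.0 | 0.7 | 6.93 | 7.80 | 5.82 |

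The k = 0.7 samples ran low on every clock. In the 3-month sample the other two came out at 3.42 and 4.30. The 2.84 is therefore sampling error, not a fault of the method. Moving the origin to first dose without delayed entry is worse than the current plan in every row, because it counts as survival time the weeks in which a late enroller could not have died and still been included.

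**The case against.** The strongest reply is that late entry is permitted but may be rare. The study is prospective, and Protocol 8.2 requires consent before any study-specific activity. The wording in Protocol 9.2 is a conditional clause in a safety-reporting section. This stands as far as frequency goes: the documents do not show that late entry is common. It does not remove the problem. Dosing here is routine practice rather than a study-specific activity, so consent need not come before dose 1, and no other section forbids later enrollment.

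Three stronger readings are tempting, and the documents do not support them.

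- A reader might infer that early treatment failures, like early deaths, are missing. Only deaths are necessarily lost. Patients who have already failed may still enroll, which is how the negative PFS times arise.
- A reader might take the 10-19% dying within 4 weeks of first dose, or a 4-week lag set against a 3-6 month median, as the size of the error in median OS. Under the constant hazard that yields those percentages, the median is not biased at all.
- A reader might conclude that the curves must look too favourable. The direction depends on the hazard shape, which is not known.

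It is also fair to say that SAP 4 sets no hypothesis and that PFS and OS are listed only under the publication tables and figures (SAP 9, Section II). That limits the consequence.

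**Conclusion.** The point holds. Followed as written, the plan mixes time origins, cannot include would-be late enrollers who die before consent, and has no rule for a PFS event dated on or before enrollment. These statements rest on the text alone.

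The size of any bias cannot be stated, because the share of late enrollers, their lag and the hazard shape are not given. Under the assumed ranges, a true 3-month median could read anywhere from 2.3 to 4.6 months and a true 6-month median from 5.1 to 8.2, with no change if the hazard is constant. If nearly all patients enroll by their first dose, the effect is negligible, but the plan does not require the report that would show this.

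A separate loss adds to it. If PFS and OS use the effectiveness set, as their place under SAP 8.2.3 implies, patients who die before any response evaluation also drop out, and changing the time origin does not bring them back.

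The consequence is confined to the descriptive curves in the manuscript. The change should be made before that analysis is run.

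**What to change.** In the PFS and OS clauses of SAP 8.2.3:

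1. Define the enrollment date, for example as the date of the signed consent or privacy statement.
2. Set time zero at the first BESPONSA administration date, with delayed entry (left truncation) into the risk set at the enrollment date for anyone who enrolls later. Make both changes together; do not move the origin alone.
3. State that a patient with a PFS event on or before entry does not enter the PFS risk set, and report how many there are. Align the PFS censoring rule that falls back on the enrollment date.
4. Report the number enrolled after first dose and the median lag.
5. Add a sensitivity analysis in patients enrolled on or before first dose.
6. Analyse OS in all eligible treated patients, without requiring a response evaluation.

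The cost is SAP wording and an entry-time option in the program. The administration dates and the privacy-statement date are already on the CRF (Protocol 7.3.6 and 7.3.1). The drawback is smaller early risk sets, and so less precise early estimates, more so among 100 patients if late entry is common. Delayed entry also assumes that the time of enrollment is unrelated to prognosis. With entry at the physician's discretion this cannot be guaranteed, which is a further reason for the sensitivity analysis.

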7.6.2. Record retention

To enable evaluations and/or inspections/audits from regulatory authorities or Pfizer, the investigator agrees to keep records, including the identity of all participating patients (sufficient information to link records, e.g., CRFs and hospital records), all original signed informed consent documents, copies of all CRFs, safety reporting forms, source documents, detailed records of treatment disposition, and adequate documentation of relevant correspondence (e.g., letters, meeting minutes, and telephone call reports). The records should be retained by the investigator according to local regulations or as specified in the clinical study agreement (CSA), whichever is longer. The investigator must ensure that the records continue to be stored securely for so long as they are retained.

If the investigator becomes unable for any reason to continue to retain study records for the required period (e.g., retirement, relocation), Pfizer should be prospectively notified. The study records must be transferred to a designee acceptable to Pfizer, such as another investigator, another institution, or to an independent third party arranged by Pfizer.

Study records must be kept for a minimum of 15 years after completion or discontinuation of the study, unless if required by applicable local regulations.

The investigator must obtain Pfizer's written permission before disposing of any records, even if retention requirements have been met.

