8.3. Patient withdrawal

Patients may withdraw from the study at any time at their own request, or they may be withdrawn at any time at the discretion of the investigator or sponsor for safety, behavioral, or administrative reasons. In any circumstance, every effort should be made to document subject outcome, if possible. The investigator should inquire about the reason for withdrawal and follow-up with the subject regarding any unresolved adverse events.

If the patient withdraws from the study, and also withdraws consent for disclosure of future information, no further evaluations should be performed, and no additional data should be collected. The sponsor may retain and continue to use any data collected before such withdrawal of consent.

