2.1 STUDY DESIGN

This is a prospective, observational, non-interventional, multi-center study in which subjects will be administered as part of routine practice at Korean health care centers by accredited physicians. The study can be performed in Korean health care centers where BESPONSA® is prescribed to treat the relapsed or refractory B-cell precursor ALL.

All subjects enrolled should meet the usual prescribing criteria for BESPONSA® as per the local product document (LPD) and should be entered into the study at the physician's discretion.

Duration of the Study

According to MFDS re-examination regulation, the re-examination report based on collected data of 6 years must be submitted to MFDS within 3 months after the end of specified re-examination period (from the product approval date to 6 years afterwards).

The data collection period of this study is until the required subject number (100 patients) is collected. The observation period for each subject is from initiating administration of first dose of BESPONSA® to the end of the observation period of the study, which must include at least 28 calendar days following the last administration of a BESPONSA®. In case of patient that Hematopoietic Stem Cell Transplant (HSCT) after administrated BESPONSA®, follow-up until 180 days after transplantation. All the data collected during the observation period should be recorded in the case report form (CRF). In case of an adverse event/safety event recognized after the observation period ends, it should be recorded in the CRF.

Sample Size

CCI

CCI

period. CCI

100 subjects will be collected during re-examination

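### Overall survival: survivors are censored at a completion/discontinuation date that is not defined per patient, while deaths count with no time limit

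*SAP*

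**What the plan says.** The OS clause is the second SAP section numbered 8.2.3.6. The note in SAP 8.2.3.7 on best overall response refers to the publication clauses as 8.2.3.8 to 8.2.3.10. OS runs from enrolment to death from any cause, and the clause sets no end to the period in which a death counts. For survivors: "For patients last known to be alive, OS will be censored at date of completion/discontinuation".

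The nearest text to a patient-level end date is the observation period. Protocol 7.2.3 runs it from the first dose to the end of the study's observation period, "which must include at least 28 calendar days following the last administration of a BESPONSA". Protocol 7.2.3 and SAP 2.1 add a separate rule for transplant: "In case of patient that Hematopoietic Stem Cell Transplant (HSCT) after administrated BESPONSA®, follow-up until 180 days after transplantation".

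On events that come to light late, Protocol 7.2.3 says: "In case of an adverse event/safety event recognized after the observation period ends, it should be recorded in the CRF". In the protocol that sentence goes on to refer to Section 7; the SAP 2.1 copy has no such reference. Protocol 8.3 says of withdrawn patients: "In any circumstance, every effort should be made to document subject outcome, if possible".

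The neighbouring clauses on progression-free survival (PFS) and duration of remission both censor at the last valid disease assessment. SAP section 9 lists an OS table and an OS figure for publication. No estimator is named; Kaplan-Meier is assumed below.

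**The concern.** A survival curve is unbiased only if the moment a patient leaves observation says nothing about that patient's risk of death, and if deaths and survivors are followed to the same point. The OS clause secures neither.

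- **Undefined date.** Two programmers could choose different censoring dates and both comply with the SAP.
- **Follow-up tied to treatment course.** If the date is individual exit, patients without transplant may leave shortly after their last dose while transplanted patients stay for months. The later part of the curve would then rest mostly on transplanted patients, whose prognosis may differ.
- **Unequal handling of late information.** A death learned of after exit fits the event definition. A survivor known to be alive at the same later time is still censored at exit.

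At stake is a published real-world survival curve for 100 patients that readers may compare with other sources.

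**Working it through.** The plan states no OS figure, event count or power for this analysis, so there is nothing to reproduce. The check compares passages and then uses a small illustration.

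**Step 1: what the date could mean.** Protocol 7.6.2, on record retention, pairs the same two words: "completion or discontinuation of the study". Study exit is therefore the natural reading, but that section gives no date for a patient. Two readings remain.

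- *Reading A, individual exit.* Let L be the day of the last dose and T the day of transplant. Guaranteed follow-up ends at L + 28 without transplant and at T + 180 with it. The difference is (T + 180) - (L + 28) = (T - L) + 152 days, so at least 152 days for any transplant on or after the last dose. The 28 days is a floor; actual follow-up may be longer.
- *Reading B, one study-level end.* Protocol 9.2 has a rule that begins "If a patient was administered a drug under study on the last day of the observation period" and extends reporting by 28 days. Such a rule has a purpose only if the observation period can end on a dosing day, which fits a study-level end. Censoring then depends on the enrolment date, not on treatment course.

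**Step 2: does Reading A bias the curve?** Illustration with 200,000 simulated patients per scenario, all censored at the minimum follow-up and no late deaths counted. Only the 3-6 month background median survival (Protocol 5, SAP 2) comes from the documents; it was used to scale the non-transplant medians of 91 and 182 days. The rest is assumed: exponential survival; time on drug with mean 60 days, capped at 168; transplant 28 days after the last dose; and the transplant-group hazard applying from the last dose.

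| Assigned to transplant | Median OS, no transplant / transplant (days) | True 182-day OS | Kaplan-Meier | Difference (points) | At risk per 100, day 182 / 365 |
|---|---|---|---|---|---|
| 40% | 182 / 182 | 0.500 | 0.499 | -0.1 | 22 / 1 |
| 20% | 91 / 365 | 0.308 | 0.386 | +7.8 | 12 / 0 |
| 40% | 182 / 91 | 0.424 | 0.365 | -5.9 | 15 / 0 |

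With equal hazards the unequal follow-up does no harm. When transplanted patients do better the curve is too high, and when they do worse it is too low. At minimum follow-up almost nobody is at risk at one year. For scale, the 95% interval at n = 100 and 50% survival is ±1.96 × √(0.5 × 0.5 / 100) = ±0.098, about 10 points.

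**Step 3: can late deaths be counted one-sidedly?** The OS clause would admit them. What the study would collect is narrower:

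- Protocol 7.3.8.2 treats progression as a serious event only when it is fatal within the safety reporting period.
- Protocol 7.3.8.3, within the Section 7 to which 7.2.3 refers, collects events that occur during the observation period. The late-recognition sentence may therefore mean late discovery of an earlier event.
- Protocol 9.2 covers the case where the investigator "becomes aware of a SAE occurring at any time after completion of the study", but only if the event is considered drug-related. The report goes to the sponsor's safety group, and that rule does not mention the CRF.

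Some late deaths could still enter: related ones, those recorded under the SAP 2.1 wording, and outcomes documented after withdrawal. Counted alone, they lower the curve, because after exit only patients who go on to die remain in the risk set.

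**The case against.** The strongest reply is that this is a wording gap in a secondary, descriptive analysis. SAP section 4 states no hypothesis and draws no definite conclusions from p-values, and OS is outside the tables for the regulator. A study-level end date is a fair reading and makes the censoring administrative. The 28 days is only a minimum. Leukaemia deaths after the reporting period are largely outside what the protocol asks sites to report. The illustrated errors rest on assumed inputs and are smaller than the 10-point sampling margin.

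Most of this stands, and it sets the severity. It does not remove the point: the clause fits two readings with different consequences, and the SAP does not choose. A confidence interval does not cover systematic error, so its width is no defence.

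Two stronger conclusions are tempting.

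- A reader might infer that late deaths will be counted one-sidedly. The rules in Protocol 7.3.8.2, 7.3.8.3 and 9.2 make this possible for some deaths, not established.
- A reader might infer that deaths cannot be dated because Protocol 7.3 lists no date-of-death item. But a fatal malignancy in the reporting period must be recorded as a Grade 5 event, and events carry onset dates. The eCRF also holds at least one item that Protocol 7.3 does not list (SAP 5.1, whether adverse event status was evaluated).

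**Conclusion.** The point holds as a minor one. The OS censoring date is undefined for a patient, and deaths and survivors are not held to a common end point. Informative censoring is possible under individual exit and is avoided under a single study-level end; counting late deaths without late survivors is possible, but the safety rules limit it.

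A reader might infer that the published curve will be too optimistic. The documents do not support that or the opposite. The net direction depends on actual follow-up beyond the 28-day floor, on survival after transplant and on capture of late deaths, none of which they give. The differences of -0.1, +7.8 and -5.9 points show only that either sign can arise under the assumptions listed; they are not estimates for this study. The OS analysis is for publication, so the OS clause does not alter the analyses for the regulator.

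**What to change.** Replace the censoring sentence in the SAP's OS clause with:

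> Patients not known to have died by [one stated data cut-off] are censored at the last date known alive on or before that cut-off. Deaths after a patient's end of observation are counted only if vital status was updated for survivors in the same way; otherwise both are cut at end of observation.

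Say in the same place whether end of observation is an individual or a study-level date, since the last part of the rule depends on it.

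With the OS figure, show numbers at risk and follow-up time by transplant status, and state the unequal minimum follow-up as a limitation. This is needed even with the new sentence: cutting deaths and survivors at the same exit removes one-sided counting but not censoring that depends on transplant.

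The cost is a SAP wording change, slightly more table work and a more cautious statement about OS. Settling the rule before the analysis also avoids a choice made after the data are seen.
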